Following study screening and baseline procedures, subjects will take the study medications daily for 16 weeks. At baseline a review of patient's daily diet will be conducted by a 24 hour food recall. Inquiries will also be made on past week's consumption of calorie-dense snack food and sugar-containing drinks. Based on a review, subjects will be instructed on how they can cut their daily calorie consumption by 500 calories. Subjects will be seen weekly for the first 4 weeks of the study, thereafter they will be seen on a bi-weekly (every other week) basis to be assessed (i.e. weight, side effect check, paper questionnaires) throughout the remaining 12 weeks of treatment. Compliance will be monitored by pill counts as well as 25mg riboflavin added to the capsules which provides florescence to urine under Wood's lamp (UV or black

HIC 1606017928

light). Subjects will be given a study identification card listing the fact that they are taking bupropion and may be taking naltrexone and this card will include the study emergency cell phone number which will be available 24 hours a day, 7 days per week in case of an emergency.

The study is planned to be run at the Connecticut Mental Health Center (CMHC).

All potential subjects will meet with study staff for intake and evaluation sessions to determine eligibility prior to enrollment. Following consent procedures, subjects' clinicians will be contacted by telephone to inform them about study participation as well as to inquire about the inclusion criteria. This has been the standard operating procedure for clinical trials conducted by this team. All participants will be carefully assessed for mood symptoms by the study psychiatrist at baseline and throughout the study duration.

A description of assessments is given below:

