- D. When and under what conditions will materials be stripped of all identifiers?
- E. Can donor-subjects withdraw their materials at any time, and/or withdraw the identifiers that connect them to their materials?
 - i. How will requests to withdraw materials be handled (e.g., material no longer identified: that is, anonymized) or material destroyed?
- F. Describe the provisions for protection of participant privacy
- G. Describe the methods for the security of storage and sharing of materials

5. **Subject Population:** Provide a detailed description of the types of human subjects who will be recruited into this study.

40 overweight/obese patients with schizophrenia.

6. **Subject classification:** Check off all classifications of subjects that will be specifically recruited for enrollment in the research project. Will subjects who may require additional safeguards or other considerations be enrolled in the study? If so, identify the population of subjects requiring special safeguards and provide a justification for their involvement.

 Children	 Healthy	 Fetal material, placenta, or dead fetus
 Non-English Speaking	 Prisoners	 Economically disadvantaged persons
 Decisionally Impaired	 Employees	 Pregnant women and/or fetuses
 Yale Students	 Females of childbearing potential	

NOTE: Is this research proposal designed to enroll children who are wards of the state as potential subjects? Yes No (If yes, see Instructions section VII #4 for further requirements)

Subjects must pass the following quiz (80% correct) in order to be eligible to consent for the study.

1. I will take study medication for 16 weeks in this study.	T X F  
2. This study aims to help me lose weight.	T X F  
3. I have to be in the study, even if I don't want to.	T   F X  
4. I will have blood drawn in this study.	T X F  
5. I should report to the study doctor if I have any side effects	T X F  
6. The study doctor and research team will know which medication I'm taking during the study.	T   F X  
7. Please circle the names of the study medication that you may receive in this study.	

Haldol

Bupropion

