The procedures, risks and benefits of the study will be discussed in detail during a face to face interview with the subject. Subjects will be given the consent form to review. Consent staff will be available in person to answer all questions at that time.

10. Evaluation of Subject(s) Capacity to Provide Informed Consent/Accent: Indicate how the personnel obtaining consent will assess the potential subject's ability and capacity to consent to the research being proposed.

Subjects with limited decision making capacity will not be enrolled. This will be determined by performance on the consent quiz as well as through discussion with their clinician and study psychiatrist.

11. Documentation of Consent/Accent: Specify the documents that will be used during the consent/assent process. Copies of all documents should be appended to the protocol, in the same format that they will be given to subjects.

Adult compound consent form for patient volunteers will be employed.

12. Non-English Speaking Subjects: Explain provisions in place to ensure comprehension for research involving non-English speaking subjects. Translated copies of all consent materials must be submitted for approval prior to use.

Non-English speaking subjects will not be enrolled

13. Consent Waiver: In certain circumstances, the HIC may grant a waiver of signed consent, or a full waiver of consent, depending on the study. If you will request either a waiver of consent, or a waiver of signed consent for this study, complete the appropriate section below.

- Not Requesting a consent waiver**
- Requesting a waiver of signed consent**
- Requesting a full waiver of consent**

A. Waiver of signed consent: (Verbal consent from subjects will be obtained. **If PHI is collected, information in this section must match Section VII, Question 6)**

- Requesting a waiver of signed consent for Recruitment/Screening only**

If requesting a waiver of signed consent, please address the following:

a. Would the signed consent form be the only record linking the subject and the research?

- Yes
- No

b. Does a breach of confidentiality constitute the principal risk to subjects?

- Yes
- No

OR

c. Does the research activity pose greater than minimal risk?

- Yes **If you answered yes, stop. A waiver cannot be granted.** Please note:

Recruitment/screening is generally a minimal risk research activity

HIC 1606017928

 No**AND**

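### The 80% consent-quiz rule makes no item mandatory, so a subject who answers that taking part is compulsory can still pass

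*Combined protocol and SAP*

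**What the plan says.** Section V, item 6 (Subject classification) gives the quiz and its rule: "Subjects must pass the following quiz (80% correct) in order to be eligible to consent for the study". There are ten numbered items.

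- Nine are true/false. Two are keyed False: item 3, "I have to be in the study, even if I don't want to", and item 6, on whether the doctor and team know the treatment.
- Items 1, 2, 4 and 5 are keyed True: "I will take study medication for 16 weeks in this study", "This study aims to help me lose weight", "I will have blood drawn in this study" and "I should report to the study doctor if I have any side effects".
- Items 8 (free to stop), 9 (withdrawal symptoms if an opiate is taken with study drug) and 10 (nausea) have lost their marks in the text available here. All three statements are true of the trial, so they are taken as keyed True.
- Item 7 is not a statement. The subject picks the possible study medications out of six names; bupropion, naltrexone and placebo are right.

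No item is marked as essential. The plan does not say how item 7 is scored or what follows a missed item.

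Section VII, item 10 says that people with limited decision-making capacity will not be enrolled, and adds: "This will be determined by performance on the consent quiz as well as through discussion with their clinician and study psychiatrist". Exclusion criterion 7 in Section V, item 7 removes those unable to give informed consent. Section V, item 3 mentions a clinician call: "Following consent procedures, subjects' clinicians will be contacted by telephone to inform them about study participation". The call also serves to ask about the inclusion criteria.

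**The concern.** A total-score rule treats all items as interchangeable. Here they are not. Items 3 and 8 ask whether the subject knows that participation is voluntary, and item 9 asks whether the subject has understood the opiate warning. Under a plain 80% rule an error on one of these costs no more than an error on whether nausea is a side effect.

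The population gives this some weight. All subjects have schizophrenia or schizoaffective disorder. Section VII, item 5 describes them as outpatients followed in the principal investigator's own clinic, and Section VII, item 3 lets research staff identify familiar patients as possible candidates. A mistaken belief that taking part is compulsory is an error the quiz ought to catch. Item 3 was written to catch it, yet the rule attaches no consequence to getting it wrong. What is at stake is participant protection; no endpoint, estimate or analysis depends on it.

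**Working it through.** The 80% is a rule, not a derived figure, so there is nothing to reproduce. The check is to score particular answer sheets against it.

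**Inputs.** Pass mark 80% (Section V, item 6). Keys: items 1, 2, 4, 5 True and 3, 6 False (printed); items 8, 9, 10 True (inferred). At one point per item (an assumption), the pass mark is 0.80 × 10 = 8.

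**Step 1: missing the voluntariness or opiate items, all else right.**

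- Item 3 missed: 10 − 1 = 9, and 9/10 = 90%, pass.
- Items 3 and 8 missed: 10 − 2 = 8, and 8/10 = 80%, pass.
- Items 3 and 9 missed: 8/10 = 80%, pass.

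These do not need the inferred keys, because a wrong answer loses the point whichever way the item is keyed.

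**Step 2: True to every true/false statement.** Seven of the nine are keyed True, so the sheet earns 7 and misses items 3 and 6.

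- Item 7 right: 7 + 1 = 8, and 8/10 = 80%, exactly the pass mark.
- Item 7 wrong or blank: 7/10 = 70%, fail.

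**Step 3: other ways of scoring item 7.** With item 7 right, the all-True sheet is simply a sheet with two true/false misses, so one column covers both.

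| Scoring | One miss | Two misses, or all-True with item 7 right | All-True, item 7 not right |
|---|---|---|---|
| One point per item (10) | 9/10 = 90% | 8/10 = 80%, pass | 7/10 = 70%, fail |
| True/false items only (9) | 8/9 = 88.9% | 7/9 = 77.8%, fail | not applicable |
| One point per correct name, no penalty (12) | 11/12 = 91.7% | 10/12 = 83.3%, pass | two names: 9/12 = 75%, fail |
| One point per name judged correctly (15) | 14/15 = 93.3% | 13/15 = 86.7%, pass | all or none circled: 10/15 = 66.7%, fail |

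A subject who misses item 3 alone passes under every scoring. A subject with two misses passes under three of the four. In the 12-point version, circling all six names would also earn full credit for item 7.

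**Step 4: guessing, one point per item.** With nine coin flips:

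- Item 7 right: P(at least 7 of 9) = (36 + 9 + 1)/512 = 46/512 = 9.0%.
- Item 7 wrong: P(at least 8 of 9) = (9 + 1)/512 = 10/512 = 2.0%.
- If each of the six names is also circled by coin flip, an exact match has probability 1/64, and P(pass) = (1/64)(46/512) + (63/64)(10/512) = 676/32,768 = 2.1%.

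The quiz as a whole therefore stops most guessing. The gap lies in which errors it tolerates.

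**The case against.** The strongest reply is that the quiz is one safeguard among several. Section VII, item 10 also relies on discussion with the clinician and the study psychiatrist. Section VII, item 9 has procedures, risks and benefits explained face to face, with staff present to answer questions. Exclusion 7 stands independently of the quiz. What staff do about a missed item may be settled elsewhere; the consent form is not in the text reviewed. All of this stands and limits the size of the point. It does not remove it: the quiz rule is explicit, and it lets an item 3 error through.

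A reader might go further in four ways that the documents do not support.

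- **That answering True throughout is enough to pass.** At one point per item it scores 7/10 and fails. The subject must also pick three medications out of six names, which agreeing with every statement does not achieve.
- **That the quiz does not screen for understanding.** Item 7 tests knowledge, and a pure guesser passes about 2% of the time.
- **That clinician input on capacity comes only after signature.** The call in Section V, item 3 is for informing the clinician and asking about inclusion criteria. It is not described as the capacity discussion or as the first contact; Section VII, item 3 allows for clinician referral beforehand. Nothing places the psychiatrist's discussion after signature. The timing is unstated, which is not a contradiction.
- **That a missed item 9 leaves subjects unprotected against opiate withdrawal.** All subjects are drug-screened (Section V, item 7), a further urine sample is taken just before randomization (Section V, item 3), and opiate users are excluded (Section V, item 9). Missing item 9 shows only that the warning was not understood.

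**Conclusion.** The point holds in a limited form. The rule requires an 80% total and no particular item. A subject who believes participation is compulsory can therefore pass under any scoring considered, at 9/10 if each item counts one point. A subject who also misses the right to stop, or the opiate warning, passes at 8/10. An all-True sheet passes only together with a correct item 7.

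The one-miss result needs no assumption about keys or about the scoring of item 7. The two-miss results assume that item 7 counts towards the total and is answered correctly; on the true/false items alone they would fail at 77.8%. The all-True result also assumes that items 8 to 10 are keyed True. Because other capacity checks exist, and urine screening covers opiate use separately, this is a cheap improvement to a protective step and not a failure of the consent process.

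**What to change.** Keep the 80% total and add that items 3, 8 and 9 must each be answered correctly before signature, with any that are missed re-explained and re-asked.

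Reverse the wording of two or three True-keyed statements, preferably among items 1, 2, 4, 5 and 10. At one point per item, two reversals leave an all-True sheet with 5 + 1 = 6/10 even with item 7 right, and 7/10 if item 3 is put right on re-asking; both fail. Three reversals give 5/10 and 6/10.

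Optionally, state in Section V, item 3 and Section VII, item 10 that the capacity discussion takes place before signature, and say how item 7 is scored.

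The cost is rewording the quiz and its rule, a few extra minutes for subjects who miss a required item, and possibly a few more people turned away. Design, sample size, treatment and analysis are untouched.

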otherwise produce separately ³²⁻³⁴. Of interest to us, the combination has been shown to be effective for clinically significant weight loss in obese subjects with type 2 diabetes as well³⁵. Registration studies by the manufacturer of the combination pill excluded antipsychotic medication users, thus we have no information on the potential effectiveness of the combination in this population. Both naltrexone and bupropion are commonly used in psychiatry, naltrexone for co-morbid alcohol addiction, and bupropion for co-morbid depression and/or cigarette addiction. The PI and the research coordinator ([name] and [name]) were also members of the Yale team that conducted a large clinical trial of bupropion for smoking cessation in schizophrenia³⁶. Thus we have extensive experience in the use of both medications in schizophrenia. Here we are proposing a 16-week pilot trial of 37.5mg naltrexone/placebo added to extended release bupropion in flexible dosing (150mg to 450mg) and a daily 500 calorie reduction diet recommendation for subjects with schizophrenia and obesity. A dose of 37.5mg is similar to the FDA-approved combination dose for naltrexone. However, based on our experience with bupropion, we have chosen to use bupropion in an unblinded manner and reach the target dose of 450mg based on tolerance of the individual subject over the initial 3-week period.

1. NASMHPD. Morbidity and Mortality in People with Serious Mental Illness. Alexandria, VA: National Association of State Mental Health Program Directors (NASMHPD); 2006.
2. Chwastiak LA, [name] C. The unchanging mortality gap for people with schizophrenia. Lancet 2009;374:590-2.

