Mellaril

Naltrexone

Paxil

Placebo

HIC 1606017928

8. I can stop being in the study any time that I want. F _____

9. If I take the study medication while taking an opiate (see list on last page) I may experience withdrawal symptoms, such as nausea, vomiting, diarrhea, muscle aches, abdominal cramping, anxiety, and sweating. F _____

10. One of the possible side effects of the study medication(s) is nausea F _____

7. Inclusion/Exclusion Criteria: What are the criteria used to determine subject inclusion or exclusion?

Inclusion Criteria

- 1) Age 18 to 75
- 2) Meet DSM-IV criteria for schizophrenia or schizoaffective disorder based on SCID interview (If bipolar-schizoaffective: need to be adequately stabilized on a mood stabilizer and show no mania history for the past one year, as confirmed by study psychiatrist and patient's clinician)
- 3) Body Mass Index (BMI) of 28 and over
- 4) On a stable dose of antipsychotic medication; i.e. at least one month with no dose change, and three months from an antipsychotic switch
- 5) Deemed to be symptomatically stable by the clinical staff in the last two months
- 6) Over 7% total body weight increase on antipsychotics for subjects within first year of illness

Exclusion Criteria

- 1) Meet criteria for current opiate abuse or dependence (confirmed by positive urine drug screen for opiates or, if suspected by study doctor via patient history and or suspicion of occult opiate use.) Note: All subjects will be screened for drugs, not only those suspected of opiate use.
- 2) A history of seizures in the past five years (confirmed through chart review and discussion with patient's clinician)
- 3) Meet DSM criteria for Bipolar Disorder
- 4) History of mania in the past one year (confirmed through chart review and discussion with patient's clinician)
- 5) Uncontrolled hypertension
- 6) Current history of dementia, mental retardation
- 7) Not capable of giving informed consent for participation in the study
- 8) Women who are pregnant or breast-feeding
- 9) Physical conditions affecting body weight (e.g. Cushing's disease, polycystic ovary syndrome)
- 10) Severe liver dysfunction, (serum aminotransferases greater than three times normal), acute infectious hepatitis, liver failure.
- 11) History of glaucoma.

8. How will **eligibility be determined, and by whom?**

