Eligibility will be determined through participant report, chart review, and communication with CMHC clinician/psychiatrist, and this will be completed by the PI and research coordinator.

HIC 1606017928

9. Risks: Describe the reasonably foreseeable risks, including risks to subject privacy, discomforts, or inconveniences associated with subjects participating in the research.

Bupropion and Bupropion/Naltrexone combination:

Small increased risk of depression, suicidal ideation, and suicide: Due to the small increased incidence of depression, suicidal ideation, attempts, and completed suicides in people having taken Naltrexone and Bupropion separately (but not in combination studies), we will monitor this risk using the Columbia Suicide Severity Rating Scale as well as regular check-ins /mood evaluations with the study psychiatrist through study participation. If, during screening or throughout the trial, a patient indicates suicidal thoughts or plans, they will be further assessed by a clinical team member or the study doctor, who will then refer the patient to their regular clinician, CMHC acute services or the YNHH emergency room, as indicated.

Risk of seizure: Bupropion can cause seizures. The risk is decreased by extended-release formulations. The extended-release formulation of bupropion that will be used in this study has a seizure incidence of 0.1%. The risk of seizure is dose-related. The incidence of seizure in patients receiving the Bupropion Naltrexone combination in clinical trials was approximately 0.1% vs 0% on placebo. The risk of seizures is also related to patient factors, clinical situations, and concomitant medications that lower the seizure threshold. We will exclude patients with any history of seizures.

Increase in Blood Pressure and Heart Rate: Bupropion alone or bupropion naltrexone combination can cause an increase in systolic and/or diastolic blood pressure as well as an increase in resting heart rate. In clinical practice with other bupropion-containing products, hypertension, in some cases severe and requiring acute treatment, has been reported. Blood pressure and heart rate in all patients, will be closely monitored throughout the trial.

Hepatotoxicity: Cases of hepatitis and clinically significant liver dysfunction has been observed with naltrexone alone at doses 10 to 12 times the study dose. No hepatotoxicity has been reported at or twice the study dose nor with the combination pill.

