The Naltrexone Bupropion combination was evaluated for safety in five double-blind placebo controlled trials in 4,754 overweight or obese patients (3,239 patients treated with THE NALTREXONE BUPROPION COMBINATION and 1,515 patients treated with placebo) for a treatment period up to 56 weeks. The majority of patients were treated with The Naltrexone Bupropion combination 32 mg/360 mg total daily dose. In addition, some patients were treated with other combination daily doses including naltrexone up to 50 mg and bupropion up to 400 mg. All subjects received study drug in addition to diet and exercise counseling. One trial (N=793) evaluated patients participating in an intensive behavioral modification program and another trial (N= 505) evaluated patients with type 2 diabetes. In these randomized, placebo-controlled trials, 2,545 patients received The Naltrexone Bupropion combination 32 mg/360 mg for a mean treatment duration of 36 weeks (median, 56 weeks). Baseline patient characteristics included a mean age of 46 years, 82% women, 78% white, 25% with hypertension, 13% with type 2 diabetes, 56% with dyslipidemia, 25% with BMI greater than 40 kg/m², and less than 2% with coronary artery disease. Dosing was initiated and increased weekly to reach the maintenance dose within 4 weeks. In The Naltrexone Bupropion combination clinical trials, 24% of subjects receiving The Naltrexone Bupropion combination and 12% of subjects receiving placebo discontinued treatment because of an adverse event. The most frequent adverse reactions leading to discontinuation The Naltrexone Bupropion combination were nausea (6.3%), headache (1.7%) and vomiting (1.1%).

The most commonly reported side effects associated with taking The Naltrexone Bupropion combination in completed clinical trials of overweight and obese individuals were: Nausea (32.5%), Constipation (19.2%), Headache (17.6%), Vomiting (10.7%), Dizziness (9.9%), Insomnia (9.2%), Dry Mouth (8.1%), Diarrhea (7.1%), Anxiety (4.2%), Hot flush (4.2%), Fatigue (4.0%), Tremor (4.0%).

In placebo-controlled clinical trials with the Naltrexone Bupropion combination for the treatment of obesity in adult patients, no suicides or suicide attempts were reported in studies up to 56 weeks in duration (equivalent to bupropion doses of 360 mg/day). In these same studies, suicidal ideation was reported by 3 (0.20%) of 1,515 patients treated with placebo compared with 1 (0.03%) of 3,239 treated with the Naltrexone Bupropion combination.

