HIC 1606017928

The incidence of seizure in patients receiving the Naltrexone Bupropion combination in clinical trials was approximately 0.1% vs 0% on placebo. The Naltrexone Bupropion combination should be discontinued and not restarted in patients who experience a seizure while being treated with Naltrexone and/or Bupropion.

The Naltrexone Bupropion combination can cause an increase in systolic and/or diastolic blood pressure as well as an increase in resting heart rate. Among patients treated with this combination medication in placebo-controlled clinical trials, mean systolic and diastolic blood pressure was approximately 1 mmHg higher than baseline at Weeks 4 and 8, similar to baseline at Week 12, and approximately 1 mmHg below baseline between Weeks 24 and 56. In contrast, among patients treated with placebo, mean blood pressure was approximately 2 to 3 mmHg below baseline throughout the same time points, yielding statistically significant differences between the groups at every assessment during this period. The largest mean differences between the groups were observed during the first 12 weeks (treatment difference +1.8 to +2.4 mmHg systolic, all $p<0.001$; +1.7 to +2.1 mmHg diastolic, all $p<0.001$). For heart rate, at both Weeks 4 and 8, mean heart rate was statistically significantly higher (2.1 bpm) in the Naltrexone Bupropion combination group compared with the placebo group; at Week 52, the difference between groups was +1.7 bpm ($p<0.001$).

In the one-year controlled trials of the Naltrexone Bupropion combination, the proportion of patients reporting one or more adverse reactions related to psychiatric and sleep disorders was higher in the Combination (32/360 mg) group than the placebo group (22.2% and 15.5%, respectively). These events were further categorized into sleep disorders (13.8% Combination, 8.4% placebo), depression (6.3% Combination, 5.9% placebo), and anxiety (6.1% Combination, 4.4% placebo). Patients who were 65 years or older experienced more psychiatric and sleep disorder adverse reactions in the Combination group (28.6%) compared to placebo (6.3%), although the sample size in this subgroup was small (56 Combination, 32 placebo); the majority of these events were insomnia (10.7% Combination, 3.1% placebo) and depression (7.1% Combination, 3.1% placebo).

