Dosing: The Naltrexone Bupropion combination should be escalated slowly, typically over a 3 to 4 week period until full dosing is reached. The Naltrexone Bupropion combination should be taken by mouth in the morning and in the evening. The tablets should not be cut, chewed, or crushed. In clinical trials, the combination was administered with meals. However, The Naltrexone Bupropion combination should not be taken with a high-fat meal because of a resulting significant increase in bupropion and naltrexone systemic exposure.

CONTRAINdications

The Naltrexone Bupropion combination is contraindicated in:

- Uncontrolled hypertension
- Seizure disorder or a history of seizures
- Use of other bupropion-containing products (including, but not limited to, WELLBUTRIN, WELLBUTRIN SR, WELLBUTRIN XL, ZYBAN, and APLENZIN)
- Bulimia or anorexia nervosa, which increase the risk for seizure
- Chronic opioid or opiate agonist (e.g., methadone) or partial agonists (e.g., buprenorphine) use, or acute opiate withdrawal
- Patients undergoing an abrupt discontinuation of alcohol, benzodiazepines, barbiturates, and antiepileptic drugs

HIC 1606017928

- Concomitant administration of monoamine oxidase inhibitors (MAOI). At least 14 days should elapse between discontinuation of MAOI and initiation of treatment with this medication combination. There is an increased risk of hypertensive reactions when the Naltrexone Bupropion combination is used concomitantly with MAOIs. Use in a patient treated with reversible MAOIs such as linezolid or intravenous methylene blue is also contraindicated
- Known allergy to bupropion and/or naltrexone
- Anaphylactic reactions and Stevens-Johnson syndrome have been reported with bupropion
- Pregnancy

3. Source: a) Identify the source of the drug or biologic to be used.

CMHC Research Pharmacy

b) Is the drug provided free of charge to subjects? Yes No
If yes, by whom? NIH grant funding

4. Storage, Preparation and Use: Describe the method of storage, preparation, stability information, and for parenteral products, method of sterilization and method of testing sterility and pyrogenicity.

Check applicable Investigational Drug Service utilized:

YNHH IDS
 CMHC Pharmacy
 PET Center
 Other:

Yale Cancer Center
 West Haven VA
 None

Note: If the YNHH IDS (or comparable service at CMHC or WHVA) will not be utilized, explain in detail how the PI will oversee these aspects of drug accountability, storage, and preparation.

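### Exclusion 2 lets in patients whose last seizure was more than five years ago, although Section V.9 says any seizure history excludes

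*Combined protocol and SAP*

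**What the plan says.** Section V.7 lists 11 exclusion criteria. Item 2 reads "A history of seizures in the past five years", to be confirmed by chart review and by discussion with the patient's clinician. No reason is given for the five-year limit.

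Section V.9, under the risk of seizure, says that bupropion can cause seizures. It adds "The risk of seizure is dose-related", and says that the risk also depends on patient factors, clinical situation and concomitant medicines. The paragraph ends with the protective measure: "We will exclude patients with any history of seizures". It sets no time limit.

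Section V.10 asks how the risks will be minimised. It answers only by referring back to what has been described above, that is, to V.9.

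Section VI.A.2 lists contraindications to the naltrexone-bupropion combination. Among them is "Seizure disorder or a history of seizures", again with no time limit.

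Section V.3 gives open-label extended-release bupropion to all subjects; only naltrexone or placebo is randomised. Section V.2 says the plan is to "reach the target dose of 450mg based on tolerance of the individual subject over the initial 3-week period".

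**The concern.** V.7 and V.9 both state what this trial will do about seizure history, and they do not state the same thing. V.9 gives the any-history exclusion as its protection against a known serious drug risk, and V.10 leans on it. If the eligibility list is narrower, that protection is not fully delivered.

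The stake is patient safety. Bupropion goes to both arms, so being allocated to placebo does not remove the exposure. Allocation is also blinded and comes after screening, so eligibility has to be acceptable for the combination in every candidate.

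**Working it through.** There is no figure in the plan to reproduce and no arithmetic to do. The check is to set the statements side by side for each type of candidate.

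| Candidate | V.7, exclusion 2 | V.9, risk of seizure | VI.A.2, contraindications (background) |
|---|---|---|---|
| Seizure within the past five years | Excluded | Excluded | Contraindicated |
| Last seizure more than five years ago | Not excluded | Excluded | Contraindicated |
| No seizure history | Not excluded | Not excluded | Not contraindicated on this ground |

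1. Only the middle row differs. The two rules for this trial, V.7 and V.9, give opposite answers there.

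2. V.7 is the operative text. Its heading asks for the criteria that determine inclusion and exclusion, and item 2 is specific enough to be applied directly: it has a window and a way of confirming it.

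3. The confirmation step does not close the gap. Chart review and a call to the clinician may well uncover a seizure from, say, eight years ago (an illustrative interval). Under item 2 as written, that finding does not exclude the patient.

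4. No other line in V.7 catches this patient. Neither the six inclusion criteria nor the other ten exclusions mention seizures.

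5. Carrying a V.9 safeguard into V.7 is what the protocol does elsewhere. V.9 says subjects with glaucoma will be excluded, and V.7 item 11 excludes a history of glaucoma with no time limit. For seizures the transfer was made with a five-year limit that V.9 does not have.

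**The case against.** The best reply is that both rules can be obeyed at once. Excluding anyone with any seizure history satisfies V.7 as well as V.9, and V.7 compels nobody to be enrolled. The principal investigator and the research coordinator complete eligibility (Section V.8) and can be expected to know V.9. The protocol is sensibly read this way for opioids: V.7 item 1 names current abuse or dependence, and V.9 more broadly excludes opiate users.

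Part of this stands. A careful investigator may well apply the stricter rule, and it cannot be said that an ineligible patient will be enrolled. But item 2 sets an explicit time limit, which tells the reader that older seizures are acceptable. A safeguard should not depend on staff overriding the criterion in front of them.

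Several stronger readings are tempting, and the documents do not support them:

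- *Two statements outvote one.* VI.A.2 is background on the combination product, not a trial enrolment rule. It supports the stricter wording, but the conflict is one trial rule against another.
- *The dose makes the problem larger.* VI.A.2 says of the combination trials that "The majority of patients were treated with The Naltrexone Bupropion combination 32 mg/360 mg total daily dose", and a reader might set that against the 450 mg target here. The comparison does not bear on who is excluded. The 450 mg is a tolerance-based target, Section V.11 describes the doses as at and below the approved dose, and no dosing error is shown.
- *Stopping after a seizure is mandatory and settles eligibility.* VI.A.2 says that the combination "should be discontinued and not restarted in patients who experience a seizure while being treated with Naltrexone and/or Bupropion". That is advice on managing a seizure during treatment and does not address past history.
- *Every labelled contraindication missing from V.7 is an error.* V.7 has no line for other bupropion-containing products or for monoamine oxidase inhibitors (MAOIs). However, medications are listed at the telephone screen to confirm eligibility, charts and clinicians are consulted, medication is checked at visits, and bupropion is open-label to the prescriber. This is missing detail, not a contradiction.

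**Conclusion.** The point holds and should be corrected: exclusion 2 is wrong as written, because it conflicts with the protocol's own stated safeguard. The defect affects candidates whose last seizure was more than five years ago, and nobody else.

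Its size cannot be given as a number. The documents do not say how many of the 40 planned subjects might fall in this group, and they give no seizure rate for patients with an earlier seizure. The 0.1% incidences in V.9 are not reported for that group. The importance comes from the seriousness of the risk and from bupropion being given to everyone, not from an expected count.

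The conclusion assumes that staff screen from V.7 and that V.9 states the intended rule. The second assumption is supported by V.10's reliance on V.9 and by the contraindication text. A reader might infer that the treatment comparison is also compromised. Nothing supports that: the rule applies before randomisation and to both arms alike.

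**What to change.** Change exclusion 2 in Section V.7 to *seizure disorder or any history of seizures*, confirmed by the chart review and clinician discussion already named there. V.9 and V.10 then need no change.

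The cost is a short amendment with no new procedure. Candidates with older seizures become ineligible under V.7, as V.9 already says they are; the documents do not give their number.

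Optional, and not part of the error: add exclusions for use of any other bupropion-containing product, and for MAOI use currently or within the previous 14 days, both checked from the medication list already collected. The first has a recruitment cost of unknown size. Section V.2 says both study drugs are commonly used in psychiatry, so the loss of existing bupropion users might matter in a 40-subject pilot.
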